	
A Gilead Data Review Committee (GDRC) analysis of Primary Cohort data will be conducted after the approximately 20 participants planned to be enrolled in the Primary Cohort reach Week 12. After GDRC review, the optional Pilot Cohort of up to 20 participants may be enrolled and will have the same treatments and assessments as the Primary Cohort.
 
Clinical and laboratory assessments including hematology, chemistry, urinalysis, pregnancy test (for women of childbearing potential), HIV-1 RNA, CD4+ cell count, CD8+ cell count, CD4/CD8 ratio, vital signs, weight, focused physical examination, eGFR, and assessment of AEs and concomitant medications will be performed at Day 1, Weeks 4, 12, 26, 38, 52, early termination (ET), and post-ET follow-up visits (note: complete physical examination will be performed at Day 1 and ET).
 
Thyroid will be assessed at screening, Day 1, Weeks 4, 12, 26, 38, and 52.
 
ECG will be performed at screening, Day 1, Weeks 26, and 52.
 
HIV-1 RNA will also be assessed at Weeks 4, 8, 12, 16, 20, 24, 26, 38, and 52.
 
HIV reservoir assays will be assessed at Day 1 (predose) and Week 52.
 
Immune biomarker will be collected at Day 1 (predose), Weeks 4, 26, 38, and 52.
 
Plasma storage sample for virology testing at all visits except screening and Days 2 and 8.
 
Serum PK samples for GS-5423 and GS-2872 will be collected at the following time points for all participants:
 
 • Day 1: 0 hour (predose, ≤ 30 minutes prior to dosing of oral LEN for loading), within 5 minutes after the end of the first antibody infusion (GS-5423) and within 5 minutes after the end of the second antibody infusion (GS-2872) • Single anytime sample at Weeks 4, 8, 12, 16, 20, 24, 26, 38, and 52 
Plasma PK samples for LEN will be collected at the following times for all participants:

--	--

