- 13) Alkaline phosphatase within normal limits;
- 14) Total bilirubin ≤ 1.5 mg/dL, or normal direct bilirubin;
- 15) Adequate hematologic function (absolute neutrophil count $\geq 750/\text{mm}^3$; platelets $\geq 50,000/\text{mm}^3$; and hemoglobin ≥ 8.5 g/dL). Those with chronic neutropenia with no clinical significance can enroll at investigator discretion;
- 16) Females of childbearing potential (as defined in [Appendix 5](#)) must have a negative serum pregnancy test at screening and negative urine pregnancy test at Day 1 prior to study drug administration;
- 17) Male and female participants of childbearing potential who engage in heterosexual intercourse must agree to utilize protocol-specified method(s) of contraception as described in [Appendix 5](#);
- 18) Female participants must refrain from egg donation and in vitro fertilization during study participation and until at least 700 days following the last dose of study drugs;
- 19) Male participants must refrain from sperm donation during treatment and until the end of the protocol-defined follow-up period.

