6.7.1. Blood Samples

Blood sample collection for the following laboratory analyses will be performed as specified:

- Proviral DNA phenotype by the PhenoSense mAb Assay DNA at Monogram Biosciences **at screening (Part 1)**
- Bulk viral outgrowth phenotype **at screening** for subsequent testing
- Proviral DNA genotype **at screening** for subsequent testing

- Hematology profile: complete blood count (CBC) with differential and platelet count at **screening, Day 1, Weeks 4, 12, 26, 38, 52, ET, and post-ET follow-up visits**
- Chemistry profile: alkaline phosphatase, AST, ALT, gamma-glutamyltransferase (GGT), total bilirubin, direct and indirect bilirubin, total protein, albumin, lactate dehydrogenase (LDH), creatine phosphokinase (CPK), bicarbonate, blood urea nitrogen (BUN), calcium, chloride, creatinine, glucose, phosphorus, magnesium, potassium, sodium, uric acid, amylase (reflex lipase testing is performed in participants with total amylase > 1.5 × ULN) at **screening, Day 1, Weeks 4, 12, 26, 38, 52, ET, and post-ET follow-up visits**
- Coagulation (prothrombin time, partial thromboplastin time, international normalized ratio) **at screening**
- Thyroid function: TSH, T3, and free T4 **at screening, Day 1, Weeks 4, 12, 26, 38, and 52**
- CD4+ cell count, CD8+ cell count, and CD4/CD8 ratio **at screening, Day 1, Weeks 4, 12, 26, 38, 52, ET, and post-ET follow-up visits**
- eGFR according to the Cockcroft-Gault formula for CL_{cr} **at screening, Day 1, Weeks 4, 12, 26, 38, 52, ET, and post-ET follow-up visits**

$$\text{Male: } \frac{(140 - \text{age in years}) \times (\text{weight in kg})}{72 \times (\text{serum creatinine in mg/dL})} = \text{CL}_{\text{cr}} \text{ (mL/min)}$$

$$\text{Female: } \frac{(140 - \text{age in years}) \times (\text{weight in kg}) \times 0.85}{72 \times (\text{serum creatinine in mg/dL})} = \text{CL}_{\text{cr}} \text{ (mL/min)}$$

- Serum follicle-stimulating hormone (FSH) test (required for female participants < 54 years of age who have stopped menstruating for ≥ 12 months but do not have documentation of ovarian hormonal failure; see [Appendix 5](#)) **at screening**
- Serum pregnancy test (females of childbearing potential only) **at screening, Weeks 4, 12, 38, 52, ET, and post-ET follow-up visits**. If the test is positive at screening, the participant will not be randomized.

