7.4.2.3. Pregnancy Reporting Process

- The investigator should report pregnancies in female study participants and/or female partners of male participants that are identified after initiation of study drug and throughout the study, including the poststudy drug follow-up period, to Gilead GLPS using the pregnancy report form within 24 hours of becoming aware of the pregnancy. Contact details for transmitting the pregnancy report form are as follows:

Gilead GLPS

Email: PPD

or

Fax: PPD

- The pregnancy itself is not considered an AE, nor is an induced elective abortion to terminate a pregnancy without medical reasons.
- All other premature terminations of pregnancy (eg, a spontaneous abortion, an induced therapeutic abortion due to complications or other medical reasons) must be reported within 24 hours as an SAE, as described in Section 7.4.1. The underlying medical reason for this procedure should be recorded as the AE term.
- A spontaneous abortion is always considered to be an SAE and will be reported as described in Section 7.4.1. Furthermore, any SAE occurring as an adverse pregnancy outcome poststudy must be reported to the Gilead GLPS.

- The participant should receive appropriate monitoring and care until the conclusion of the pregnancy. The outcome of the pregnancy/partner pregnancy should be reported to Gilead GLPS using the pregnancy outcome report form. If the end of the pregnancy/partner pregnancy occurs after the study has been completed, the outcome should be reported directly to Gilead GLPS. Gilead GLPS contact information is as follows: email: PPD and fax: PPD
- Refer to [Appendix 5](#) for Pregnancy Precautions, Definition for Female of Childbearing Potential, and Contraceptive Requirements.

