Appendix 2. Study Procedures Table

Study Procedure	Screening ^a	Day 1	Treatment Visits Window (± 3 Days)											Follow-up Visits Window (± 6 Days)	
			Day 2	Day 8	Wk 4	Wk 8	Wk 12	Wk 16	Wk 20	Wk 24	Wk 26	Wk 38	Wk 52	ET	Post-ET 30-, 90-, and 180- Day FU ^b
Written Informed Consent	X														
Medical History	X														
Review Concomitant Medications	X	X	X	X	X	X	X	X	X	X	X	X	X	X	X
Review AEs	X	X	X	X	X	X	X	X	X	X	X	X	X	X	X
Complete Physical Examination	X	X												X	
Focused Physical Examination					X		X				X	X	X		X
Height	X														
Weight	X	X			X		X				X	X	X	X	X
Vital Signs ^c	X	X			X		X				X	X	X	X	X
Proviral DNA Phenotype	X														
Bulk Viral Outgrowth Phenotype and Proviral DNA Genotype	X														
Chemistry	X	X			X		X				X	X	X	X	X
Hematology	X	X			X		X				X	X	X	X	X
Coagulation	X														
Thyroid Function	X	X			X		X				X	X	X		
CD4+, CD8+ Cell Count, CD4/CD8 Ratio	X	X			X		X				X	X	X	X	X

[figure not shown]
Study Procedure	Screening ^a	Day 1	Treatment Visits Window (± 3 Days)											Follow-up Visits Window (± 6 Days)	
			Day 2	Day 8	Wk 4	Wk 8	Wk 12	Wk 16	Wk 20	Wk 24	Wk 26	Wk 38	Wk 52	ET	Post-ET 30-, 90-, and 180- Day FU ^b
Serum Pregnancy Test	X				X		X					X	X	X	X
FSH ^d	X														
Urinalysis	X	X			X		X				X	X	X	X	X
Urine Pregnancy Test		X													
HBV & HCV Serology	X														
HIV-1 RNA	X	X			X	X	X	X	X	X	X	X	X	X	X
HIV-1 Genotype/Phenotype ^e															
HIV Reservoir Assay		X											X		
eGFR	X	X			X		X				X	X	X	X	X
ECG	X	X									X		X		
Immune Biomarker Collection		X			X						X	X	X		
Plasma Storage Samples for Virology Testing		X			X	X	X	X	X	X	X	X	X	X	X
Immunogenicity Assessment Serum Sample		X			X		X				X	X	X		
PD Biomarkers: PBMC, Whole Blood, Serum, Plasma		X			X						X	X	X		
Serum PK samples (GS-5423 & GS-2872) ^f		X												X	X
Plasma PK Sample for LEN ^g		X												X	X
Single PK Sample (GS-5423 & GS-2872)					X	X	X	X	X	X	X	X	X		

Study Procedure	Screening ^a	Day 1	Treatment Visits Window (± 3 Days)											Follow-up Visits Window (± 6 Days)	
			Day 2	Day 8	Wk 4	Wk 8	Wk 12	Wk 16	Wk 20	Wk 24	Wk 26	Wk 38	Wk 52	ET	Post-ET 30-, 90-, and 180- Day FU ^b
Single Plasma PK Sample for LEN					X	X	X	X	X	X	X	X	X		
Optional PK Substudy Sample		X	X	X											
Randomization		X													
LEN Oral Administration ^h		X	X												
LEN SC Administration ⁱ		X													
GS-5423 IV Infusion Administration ⁱ		X													
GS-2872 IV Infusion Administration ⁱ		X													

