GS-2872 and GS-5423 are contraindicated in pregnancy as their teratogenicity/fetotoxicity profile is unknown. A reduction in the clinical efficacy of hormonal contraception is not expected as GS-2872 and GS-5423 are not cytokine modulators. As protein biologics, GS-2872 and GS-5423 are not expected to be genotoxic but genotoxicity has not been evaluated in these compounds and so conservative contraceptive requirements are used in this study. Refer to the latest version of the investigator's brochure (IB) for additional information.

b) Contraception Requirements for Female Born Participants of Childbearing Potential

The inclusion of female born participants of childbearing potential requires using at least an acceptable effective contraceptive. They must have a negative serum pregnancy test at screening and a negative pregnancy test at the Day 1 visit prior to the dose of study drug. Pregnancy tests will be performed as defined by the study procedures in [Appendix 2](#). In the event of a delayed menstrual period (over 1 month between menstruations), a pregnancy test must be performed to rule out pregnancy. This is even true for female born participants of childbearing potential with infrequent or irregular periods. Female born participants of childbearing potential must agree to 1 of the following from screening until 700 days following the last dose of study drug:

Complete abstinence from intercourse of reproductive potential. Abstinence is an acceptable method of contraception only when it is in line with the participant's preferred and usual lifestyle.

Or

Consistent and correct use of 1 of the following methods of birth control listed below:

- Intrauterine device (IUD) with a failure rate of < 1% per year
- Tubal sterilization
- Essure® microinsert system (provided confirmation of success 3 months after procedure)
- Vasectomy in the male born partner (provided that the partner is the sole sexual partner and had confirmation of surgical success 3 months after procedure)
- Barrier methods (one female barrier and one male barrier must be used in combination):
 - Female barriers: Diaphragm with spermicide or Cervical cap with spermicide
 - Male barriers: Male condom (with or without spermicide)
- Hormonal Methods that are not taken orally (each method must be used with a barrier method, preferably male condom):
 - Intrauterine hormone-releasing system (IUS) with a failure rate of < 1% per year
 - Injectable progesterone

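### The Week 26 pregnancy test is in the synopsis but missing from the schedules sites follow, leaving 26 weeks without a scheduled test; new-pregnancy reporting also ends well before the 700-day contraception period

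*Protocol*

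**What the plan says.** **Testing.** The synopsis lists the pregnancy test with hematology, chemistry and other assessments that "will be performed at Day 1, Weeks 4, 12, 26, 38, 52, early termination (ET), and post-ET follow-up visits". SAP 1.2.5.3 repeats that sentence. The item-level text in protocol 6.7.1 gives the serum test "at screening, Weeks 4, 12, 38, 52, ET, and post-ET follow-up visits", without Week 26. In protocol Appendix 2 and SAP Appendix 1, the row "Serum Pregnancy Test" is marked at screening, Weeks 4, 12, 38 and 52, early termination (ET) and post-ET, and is empty at Week 26. The urine test (6.7.2) is on Day 1 only. Appendix 5 settles which schedule governs: "Pregnancy tests will be performed as defined by the study procedures in" Appendix 2. It also requires an unscheduled test when a period is delayed, and asks participants to tell the investigator of a known or suspected pregnancy.

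**Reporting.** Under Appendix 5, female participants of childbearing potential "must agree to 1 of the following from screening until 700 days following the last dose of study drug". Inclusion criterion 18 restricts egg donation and in vitro fertilization "until at least 700 days following the last dose of study drugs". Section 7.4.2.3 asks investigators to report pregnancies "identified after initiation of study drug and throughout the study, including the poststudy drug follow-up period". It adds that "The pregnancy itself is not considered an AE", while outcomes of pregnancies already known and serious adverse pregnancy outcomes after the study remain reportable.

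**The concern.** The documents contradict each other on whether a Week 26 test exists, and the version that omits it is the one sites are told to follow. It looks like an omission: every other assessment in the synopsis sentence is marked at Week 26 in Appendix 2, and no reason is given for leaving this one out.

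The stake is detection, not prevention, since all study drug is given on Days 1 and 2. At Week 26 every participant restarts an oral antiretroviral regimen, either the baseline one or another chosen by the investigator, and no scheduled test since Week 12 shows pregnancy status at that decision. A pregnancy starting soon after Week 12 could go nearly 26 weeks without a scheduled test. During that time SAP 3.8.1 treats exposure to all three drugs as continuing, and Appendix 5 says the fetal effects of both antibodies are not known.

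The reporting point is smaller. The sponsor asks women to avoid pregnancy for 700 days but does not ask to hear of a new pregnancy found after follow-up ends, unless the outcome is adverse.

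**Working it through.** **1. The five statements of the pregnancy-test schedule**

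| Source | Visits | Week 26? |
|---|---|---|
| Protocol synopsis | Day 1, Weeks 4, 12, 26, 38, 52, ET, post-ET | Yes |
| SAP 1.2.5.3 | Same sentence | Yes |
| Protocol 6.7.1 (serum) | Screening, Weeks 4, 12, 38, 52, ET, post-ET | No |
| Protocol Appendix 2 (serum row) | Same as 6.7.1 | No |
| SAP Appendix 1 (serum row) | Same as 6.7.1 | No |

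The empty cell is not a fault of table extraction. Read across the 15 columns, the chemistry row carries a mark at Week 26 and the serum pregnancy row does not, and the running text of 6.7.1 agrees. Week 26 is the only scheduled visit with chemistry and hematology blood that has neither a serum nor a urine pregnancy test.

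**2. Intervals between scheduled tests**

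Nominal days from SAP Table 3-3: Week 12 = 84, Week 26 = 182, Week 38 = 266, Week 52 = 364. The visit window is ±3 days (Appendix 2).

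- As written, Week 12 to Week 38: 266 − 84 = 182 days = 26 weeks. With both windows: 182 ± 6, so 176 to 188 days.
- With Week 26, Week 12 to Week 26: 182 − 84 = 98 days = 14 weeks (92 to 104).
- With Week 26, Week 26 to Week 38: 266 − 182 = 84 days = 12 weeks.
- Existing Week 38 to Week 52: 364 − 266 = 98 days = 14 weeks.

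From Day 1 onward the intervals are 4, 8, 26 and 14 weeks as written, and 4, 8, 14, 12 and 14 weeks with Week 26 added. The longest falls from 26 to 14 weeks, equal to an interval the plan already accepts.

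**3. Reporting period against contraception period**

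- Last dose: oral lenacapavir on Day 2 (protocol 5.3).
- End of contraception period: 2 + 700 = Day 702.
- Last visit for a completer: Week 52, nominal Day 364.
- Shortfall: 702 − 364 = 338 days; with ±3 days at Week 52, 335 to 341.

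Counting from the Day 1 dose, or placing Week 52 at Day 365, gives 336 to 337 days. For early terminators who attend the 180-day post-ET visit, the figure depends on when they leave:

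- ET at Week 26: 702 − (182 + 180) = 340 days.
- ET just before Week 52: 702 − (364 + 180) = about 158 days.

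**The case against.** The strongest reply is that sites already have one consistent operational schedule. Section 6.7.1 and Appendix 2 agree, Appendix 5 names Appendix 2, and the synopsis sentence merely bundles a dozen assessments against one visit list. SAP 1.2.5.3 copies that sentence and is not independent evidence of intent, so the contradiction could equally be cured by correcting the synopsis. That is true. Adding the test, and not deleting the mention of it, is a design judgement, which rests on the ART restart and the length of the interval.

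The gap is also in scheduled tests only. A delayed period triggers a test, even for women with irregular cycles, and adverse events and medications are reviewed at Weeks 16, 20, 24 and 26. These safeguards stand, and 26 weeks without a scheduled test does not mean 26 weeks undetected. But they rely largely on the participant noticing and speaking up, and the plan schedules tests at other visits despite them.

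The ART argument has limits. The default is the participant's own baseline regimen, the documents do not say pregnancy would change the choice, and restarts after virologic failure carry no linked test either. On risk, Appendix 5 reports no adverse fertility or embryo-fetal findings for lenacapavir in nonclinical studies, does not expect the antibodies to be genotoxic, and requires contraception. All of this keeps the point modest, as does the study's size: about 20 participants plus up to 20, with only females of childbearing potential affected and no count of them given.

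On reporting, the length of the follow-up period is never stated, so 338 days is an interpretation that applies to completers. The outcomes that matter most for safety are already reportable.

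**Conclusion.** The concern holds. As written, the governing schedules omit a Week 26 pregnancy test that the synopsis and SAP 1.2.5.3 say is performed. The longest interval between scheduled tests is 26 weeks (182 days, at most 188 within the visit windows), against 14 weeks with the test included. This rests on nominal visit days and on participants followed without early termination; those who leave early are tested at ET and at in-clinic post-ET visits. It is a safety-schedule inconsistency worth correcting. It does not bear on sample size, power, any endpoint or any analysis.

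The reporting gap of about 338 days is real for completers, on the natural reading that the follow-up period means protocol follow-up. What goes unreported is narrow: a new pregnancy without an adverse outcome, found after follow-up but within 700 days of the last dose. On its own it would be an optional improvement.

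**What to change.** Main change, by protocol amendment: add Week 26 to the serum pregnancy test line in 6.7.1, so that it reads screening, Weeks 4, 12, 26, 38, 52, ET and post-ET, and mark the Week 26 cell of that row in protocol Appendix 2. Then mark the same cell in SAP Appendix 1, so that it mirrors the amended protocol and does not run ahead of it. The cost is one serum test per female of childbearing potential, on blood already drawn at that visit, plus one line and two table cells. SAP 2.2 reports the Primary Cohort Week 26 analysis as already conducted, so the test can be added only for any remaining Pilot Cohort visits and for later studies reusing this schedule. The documents should be reconciled in any case.

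Secondary change: in 7.4.2.3 and in section 5 of Appendix 5, extend passive reporting of new pregnancies in female participants to 700 days after the last dose, and instruct participants accordingly at their last visit. This costs one sentence in two places and leaves sites with a passive duty for about 11 more months.

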6.7.2. Urine Samples

Urine samples will be collected for the following laboratory analyses at every study visit, unless otherwise specified:

- Urinalysis: including color and clarity, specific gravity, pH, glucose, ketones, bilirubin, urobilinogen, blood, nitrite, leukocyte esterase and microscopic (if microscopic elements are seen), urine protein, albumin, creatinine, phosphate, calcium, magnesium, and uric acid **at screening, Day 1, Weeks 4, 12, 26, 38, 52, ET, and post-ET follow-up visits**
- Urine pregnancy test predose (females of childbearing potential only) **on Day 1.**
 - If the test is positive, confirmatory serum test should be performed and study drug dosing should be delayed until results obtained

6.7.3. Blood and Urine Storage Samples

Any residual blood and urine samples collected at all visits (except the screening and ET visits) will be frozen and stored. These stored blood and urine samples may be used by Gilead or its research partners for HIV-1 genotyping/phenotyping assays or their development, for retesting the amount of HIV-1 in the blood, for measurement of antiviral drug levels in the blood, or for future testing to learn more about how the study drug has worked against HIV-1 or clinical laboratory testing to provide additional safety data. No human genetic testing will be performed without expressed consent of study participants. At the conclusion of this study, these samples may be retained in storage by Gilead for a period up to 15 years.

6.8. Management of Virologic Rebound and Virologic Failure

Virologic failure is defined as having a rebound of HIV-1 RNA ≥ 200 copies/mL at 2 consecutive visits on or before Week 26, at Week 26, or at study drug discontinuation. Participants who meet criteria for VF will have samples sent for genotypic and phenotypic testing, will restart their baseline ARV regimen (or compatible regimen selected by the investigator), and will continue study follow-up but will not receive additional doses of the study regimen.

6.8.1. Virologic Rebound

Participants who meet the criteria listed below will be considered to have VR (see [Figure 6-1](#)):

- At any post-Day 1 visit, a rebound in HIV-1 RNA ≥ 50 copies/mL that is subsequently confirmed at the following scheduled or unscheduled visit; OR
- Any participant with HIV RNA ≥ 50 copies/mL at study discontinuation or Week 26

At any post-Day 1 visit, if the HIV-1 RNA is ≥ 50 and < 200 copies/mL, a reflex HIV-1 RNA repeat test will be conducted on stored plasma samples by the study central laboratory, if available. If the repeat result is < 50 copies/mL, participants will resume scheduled study visits. If the repeat result is ≥ 50 copies/mL, participants will be asked to return to the clinic for a scheduled or unscheduled HIV-1 RNA retest (approximately 2 to 3 weeks after the date of the last test that resulted in HIV-1 RNA ≥ 50 copies/mL) for confirmation.

- HIV-1 RNA < 50 copies/mL at the confirmation visit: participants will resume scheduled study visits
- HIV-1 RNA ≥ 200 copies/mL at one visit except at study discontinuation or Week 26: participants will be asked to return to the clinic for a scheduled or unscheduled HIV-1 RNA (within 2 to 3 weeks after the date of last HIV-1 RNA) and resume scheduled study visits until confirmation results are available
- Participants with HIV-1 RNA ≥ 200 copies/mL at two consecutive visits or at study discontinuation or Week 26 meet criteria for VF, refer to [Section 6.8.2](#).
- Participants with HIV-1 RNA between ≥ 50 and < 200 copies/mL at both the confirmation visit and the previous test, must be discussed with medical monitor.

[figure not shown]
